---

**PI Name: [name]., R.D.,**

**Co-Investigator: [name].**

**Co-Investigator: [name].**

**Co-Investigator: [name]., Ph.D.**

**Medical Investigator: [name].**

**Protocol Version Date: July 24, 2018**

## OVERVIEW

The discovery that humans possess functional depots of brown adipose tissue (BAT) sparked exploration of ways to activate BAT and promote the conversion of white adipose tissue (WAT) to the brown phenotype known as beige or brown adipocytes. The accumulation of beige adipocytes in WAT, referred to as browning, has garnered interest in research on obesity because it engenders adaptive thermogenesis, a process by which the production of adenosine triphosphate (ATP) is uncoupled from the catabolism of lipids and carbohydrates. The process is mediated by uncoupling protein 1 (UCP1) which mediates resolution of the proton-motive force generated by substrate oxidation, without the synthesis of ATP. Rather, the proton gradient is liberated as heat. This type of metabolically active and energy dissipating tissue offers a potentially effective solution to counteract excessive fat accumulation, especially since BAT is typically low in humans and correlates inversely with body mass index. Among the gene regulatory pathways implicated in the thermogenic program is the nuclear receptor, peroxisome proliferator-activated receptor (PPAR $\gamma$ ), its coactivator PGC-1 $\beta$  and the transcription factor carbohydrate response element binding protein (ChREBP).

The discovery and characterization of ChREBP unraveled the main mechanism by which the transcriptional response to glucose is mediated. Increased *de novo* lipogenesis in fat provides a reservoir for excess energy and maintains glucose homeostasis. The insulin-sensitive glucose transporter type 4 (GLUT4) is the rate limiting protein for shuttling glucose, the substrate for *de novo* lipogenesis, into adipocytes. Although adipose tissue is not the major site for glucose disposal, mice with adipose-specific GLUT4 overexpression display improved glucose control, whereas adipose specific GLUT4 deficient mice develop insulin resistance and hyperglycemia. Of interest is the upregulation of ChREBP that accompanies enhanced glucose flux in adipocytes of overexpressing GLUT4. High fat feeding causes an early reduction in the expression of ChREBP in mouse adipocytes and is due in part to a decrease in GLUT4 expression. Increased ChREBP expression in adipose tissue and not liver mediates the effects on glucose homeostasis. Thus, *de novo* lipogenesis predicts metabolic health in a tissue-specific manner.

[figure not shown]
Strategies to enhance adipose tissue glucose uptake and restore depleted levels of ChREBP expression can be particularly beneficial to individuals with obesity and insulin resistance. Naringenin belongs to a class of flavonoids known as flavanones and is found in grapefruit, oranges, and limes. Naringenin has been shown to reduce diet-induced weight gain in rodents and improve glucose and lipid metabolism in a number of studies in animal and in vitro models. Activation of adenosine monophosphate-activated kinase (AMPK), regulation of insulin signaling pathways and lipid metabolism, and relief from oxidative stress in pancreatic beta cells are among the mechanisms that have been implicated. Although most of the effects of naringenin have been shown in the liver, muscle, and islet cells, increases in energy expenditure and activation of brown fat has been demonstrated in mice fed a high-fat diet supplemented with naringenin. Our in vitro studies in differentiated human subcutaneous adipose-derived stem cells from overweight and obese female donors show that naringenin stimulates mRNA and protein expression of UCP1, GLUT4 and ChREBP, key determinants of thermogenesis, systemic insulin sensitivity, and glucose homeostasis.

The effects of naringenin have primarily been demonstrated in vitro and in animal studies but only through human intervention trials can the significance to human physiology be determined. The overarching aim of the study is to conduct a randomized controlled trial to determine the safety and tolerability of naringenin in humans.

## BACKGROUND AND SIGNIFICANCE

Overexpression of ChREBP in mice fed a western diet enhances systemic insulin sensitivity, reduces fat mass and increases expression of the genes associated with thermogenesis

suggesting a role for ChREBP in whole body insulin sensitivity and brown adipose tissue function. In this type of metabolically active tissue glucose uptake is stimulated. ChREBP is a transcription factor that is known to be expressed as  $\alpha$  and  $\beta$  alternatively spliced isoforms. In humans, expression of both ChREBP $\alpha$  and  $\beta$  isoforms in white adipose tissue correlates with insulin sensitivity; but, obesity is associated with a reduction specifically in ChREBP $\beta$  expression. ChREBP is highly expressed in active sites of de novo lipogenesis including the liver, and white and brown adipose tissue. ChREBP is a key mediator of the beneficial effects of enhanced glucose uptake in adipocytes through its specific control of lipogenic genes; however, the effects of adipose ChREBP on glucose homeostasis are not simply attributed to the clearance of glucose from circulation. In an elegant study published in 'Cell,' it was discovered that adipose tissue of mice overexpressing GLUT4 in adipocytes have branched fatty acid esters of hydroxy fatty acids (FAHAs). These novel fatty acids contribute to overall insulin sensitivity by enhancing glucose uptake in adipocytes and by stimulating direct and GLP-1-mediated improvement in beta cell function. FAHAs have been shown to act via the G protein coupled receptor120 (GPR120^20) (Figure 1)

[figure not shown]
**Figure 1.** ChREBP links lipogenesis to insulin sensitivity in adipocytes. ChREBP is a key mediator of the beneficial effects of enhanced glucose uptake in adipocytes through its specific control of lipogenic genes. Branched fatty acid esters of hydroxy fatty acids (FAHAs), were found to contribute to overall insulin sensitivity by stimulating glucose transport in adipocytes and by enhancing both GLP-1 and insulin secretion. FAHAs were shown to act via the GPR120 receptor. *Physiology*. 2015;30(6):428-437.

In humans, grouped according to their two-hour blood glucose concentrations (<120mg/dL, 120-140 mg/dL, and >140 mg/dL) during an oral glucose tolerance test, the expression of GLUT4, lipogenic genes and ChREBP measured in subcutaneous fat biopsies was significantly decreased as blood glucose concentrations rose across the groups. Interestingly, expression of adipose ChREBP correlated with expression of GLUT4, lipogenic genes, 2-hour blood glucose, and insulin sensitivity measured by the euglycemic hyperinsulinemic clamp method. Although this study was done in obese adolescents, it provides preliminary evidence that ChREBP and GLUT4 gene expression correlate with physiologic outcomes related to glucose homeostasis.

Weight cycling is known to result in exacerbated post-dieting weight regain. In predisposed mice placed on a weight cycling protocol, naringenin attenuated weight regain. (Figure 2A). Figure 2B shows weight loss in subjects given one-half of a grapefruit three times/day for 12 weeks.

## Clinical Implications

Lifestyle interventions promote weight loss, reduce the conversion of impaired glucose tolerance to diabetes and are recommended as the primary approach to prevent and treat obesity and its comorbidities. However, for many people adherence to a diet and exercise regimen is particularly daunting, especially over the long term. Pharmacologic interventions such as metformin and pioglitazone reduce the risk of conversion to type 2 diabetes by 31% and 72% respectively, but, according to the American Diabetes Association's assessment of trials in prediabetes pharmacologic interventions, these benefits are not without adverse effects. Naringenin is a component of food with therapeutic potential to improve glucose metabolism. **In order to explore the mechanisms by which naringenin may increase energy expenditure and improve glucose metabolism in humans**, it is of vital importance that the safety and tolerability of naringenin is evaluated when administered to humans.

**Figure 2 A.** Weight loss in weight cycling mice. Mice placed on a cycling high fat diet (second cycle) supplemented with naringenin (orange line) gained as much weight as mice on the first cycle of a high fat diet (green line) and less weight than the mice on a cycling high fat diet (second cycle) that was not supplemented with naringenin (red line) (Nature 2016, 540:26-29). **B.** Weight loss in humans given grapefruit for 12 weeks (J Med Food 2006, 9:49-54).

## STUDY DESIGN

This is a placebo-controlled, ascending treatment crossover design trial with washout periods of at least one week.

**Primary objective:** Evaluate the effect of single oral administration of naringenin at four escalating doses on safety and tolerability in healthy volunteers.

**Secondary objective:** Evaluate the pharmacokinetics of naringenin at low (150 mg) and high (600 mg) doses to test if changes in serum concentrations are proportional to the dose, by assessing naringenin drug exposure ( $AUC_{0-24}$ ).

### Rationale for Naringenin Dose

In a human subjects study, the pharmacokinetics of naringenin has been investigated after a 135 mg dose of naringenin, administered orally. The study population included six healthy adult volunteers (five males, one female). All subjects were in good health as assessed by medical history, clinical examination, blood pressure and standard biochemical health measures. After an overnight fast subjects each subject received a single oral dose (capsule) of 135 mg of naringenin. Blood was drawn to evaluate pharmacokinetics over a 12 hour period. All six subjects successfully completed the pharmacokinetic study and none reported undesirable or adverse effects after oral administration of naringenin. All subjects who participated in the study were discharged in good health. A study completed by Harvard University and reported on ClinicalTrials.gov (NCT01091077) administered a single, 1000mg oral dose of naringenin mixed

with 16 grams of hydroxypropyl-β-cyclodextrin to enhance bioavailability. Eighteen subjects with hepatitis C viral infection were included in the study, with the primary aim of determining the safety and pharmacokinetics of naringenin. The study was conducted at the Massachusetts General hospital. There were no adverse events reported per communication with the principal investigator [name]., Harvard University School of Medicine (Appendix II).

Using the serum concentrations achieved in the only reported human pharmacokinetic study, we conducted in vitro experiments in differentiated human subcutaneous adipose-derived stem cells from an overweight female donor and from an obese female donor and showed that naringenin (7-day treatment) acts in adipose tissue to stimulate thermogenesis and insulin sensitivity. Our methods have been validated using tissue from a donor matched for body mass index and cultured at the LSU Health Sciences System (New Orleans) in a microphysiologic system that allows the cells to be viable for two weeks (unpublished data). Due to the short half-life of naringenin ( $t_{1/2} = 2.31 \pm 0.4h$ ), we hypothesize that multiple dosing up to 600 mg will be necessary for effective duration of action. Thus, it is vital that the safety of naringenin is evaluated when administered to humans at higher doses.

The maximum recommended starting dose (MRSD) for naringenin may be estimated at approximately 135 mg since no adverse events were reported at this dose. The dose escalation scheme recommended for first in human studies is rapid dose escalation initially (MRSD x 2) until the estimated effective dose (600 mg) is reached and then at a more cautious escalation (e.g. x 1.5). The first dose will be 150 mg, the MRSD for the practical purpose of preparing the capsule of an extract from oranges which contains 30% naringenin (Gencor Lifestage Solutions, GE Nutrients Inc., Irvine, CA). HPLC and mass spectrometry verification using a second standard to quantify the naringenin in the extract was conducted by the Rutgers University Botanical core. It was determined that the extract contains 27% naringenin by one method and 29% naringenin by a second method. Therefore, the amount of extract for the 150 mg, 300 mg, 600 mg, and 900 mg doses of naringenin will be calculated based on the average of 28%. According to the United States Department of Agriculture (USDA) database for the flavonoid content of selected foods 150 mg of naringenin could be found in a minimum of approximately four oranges and a maximum of 12 oranges. The orange extract will be calculated to deliver 150 mg, 300 mg, 600 mg, and 900 mg of naringenin. The capsules will be prepared and dispensed by the PBRC pharmacist. The schedule for dosing is provided in Table 1.

Table 1. Ascending Oral Dose Schedule			
	Visit 1	Visit 2	Visit 3
Cohort 1			
Sequence 1 (n=3)	150 mg	Placebo	300 mg
Sequence 2 (n=3)	150 mg	300 mg	Placebo
Sequence 3 (n=3)	Placebo	150 mg	300 mg
Cohort 2			
Sequence 4 (n=3)	600 mg	Placebo	900 mg
Sequence 5 (n=3)	600 mg	900 mg	Placebo
Sequence 6 (n=3)	Placebo	600 mg	900 mg

**Study Subjects**

This study will enroll 18 healthy adult male and female subjects. Subjects will be enrolled on the basis of the following eligibility criteria:

Inclusion Criteria

- Adult (≥18 years)

- Body mass index (determined at the screening visit) between 20 and 35 kg/m^2
- No evidence of diabetes (fasting blood sugar <126 mg/dL)
- Willing to refrain from consuming citrus fruits and tomato in any form, for 36 hours prior to each test day. Subjects will be provided a list of foods to avoid (Appendix I).

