#### Visit 1 (13 hours, fasting for at least 8 hours)

To start the study, eligible subjects will arrive at the clinic in the morning following an overnight fast (except for water) that began no later than 8 hours prior to the study appointment. The following tests and measurements will be performed:

- Weight, vital signs (blood pressure, pulse, and temperature).
- Blood collection for a CBC and Chemistry 15 panel.

- Subjects will be given a 150 mg dose of naringenin or placebo, administered orally.
- Blood collection for pharmacokinetic study of 150 mg dose of naringenin at 2, 3, 3.5, 4, 4.5, 6, 8, and 12 hours.
- Subjects will be provided a meal 5 hours after naringenin administration and at the end of the pharmacokinetic testing.

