## **STATISTICAL CONSIDERATIONS**

As comparative efficacy of the doses of the extract is not the primary issue in this protocol, power to detect efficacious effects is not specifically evaluated to justify sample sizes. A sample of 18 subjects (three subjects in each of three treatment sequences in each of two cohorts) will be enrolled in the ascending single dose evaluation. Thus, all nine subjects in Cohort 1 will receive the placebo and both 150 and 300 mg doses of the extract; similarly all 9 subjects in Cohort 2 will receive the placebo and both 600 and 900 mg doses of the extract. Before the next cohort is commenced, subjects in the preceding cohort must have received all three treatments and the safety and tolerability data must have been assessed showing tolerance to the doses of naringenin. Based on the pharmacokinetic study done in humans, the sample size (n=6, at each dose) is sufficient to provide a pharmacokinetic profile of naringenin in serum.

The primary outcome will be to determine the effect of the naringenin extract on safety and tolerability based on clinical and biochemical assessment.

The secondary outcome will be to determine the pharmacokinetics of naringenin at the 150 mg and 600 mg doses. Serum concentrations of naringenin will be obtained to assess drug exposure.

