### Stopping Rules

Dosing within a cohort will be stopped and further dosing will be halted until un-blinded safety information can be reviewed in the event that:

- A death occurs
- Two or more subjects experience the same SAE following administration of study product.
- Two or more subjects in each cohort experience the same severe study product-related AE following administration of study product
- Based on AEs, laboratory findings, or clinical findings the Investigator determines that review of pertinent safety information is required.

Dosing may only resume if, after review of safety information, both the Investigator and IRB agree that it is safe to proceed.

**Pharmacokinetics of naringenin extract.** Pharmacokinetics of orally administered naringenin will be analyzed using a non-compartmental model. The maximal concentration ( $C_{max}$ ), time to peak ( $T_{max}$ ), half-life ( $T_{1/2}$ ), area under the serum concentration versus time curve ( $AUC_{0-24hr}$ ) and apparent oral clearance ( $Clearance_{oral} = Dose/AUC_{0-24hr}$ ) for each subject will be determined and the means for subjects given 150 mg and 600 mg doses will be calculated. Pairwise comparisons of 150 mg, 600 mg and placebo will be tested with a linear model for each of the parameters ( $C_{max}$ ,  $T_{max}$ ,  $T_{1/2}$ ,  $AUC_{0-24hr}$  and  $Clearance_{oral}$ ) across all time points. All analyses will use SAS Version 9.4 software (SAS Institute Inc., Cary NC).

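### Exposure at 150 and 600 mg is compared between different people with no weight term: only noise if the cohorts are alike, a moderate bias if they differ, so a supportive weight-adjusted analysis is worth pre-specifying

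*Combined protocol and SAP*

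**What the plan says.** All places are in the combined protocol and SAP.

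- **Objective (Study Design).** The secondary objective uses AUC0-24 at 150 and 600 mg "to test if changes in serum concentrations are proportional to the dose".
- **Dose basis (Rationale for Naringenin Dose).** Doses are absolute amounts, not per kilogram: "The orange extract will be calculated to deliver 150 mg, 300 mg, 600 mg, and 900 mg of naringenin".
- **Body size (Study Subjects).** The criterion is "Body mass index (determined at the screening visit) between 20 and 35" kg/m², for men and women, with no weight limit or weight stratum.
- **Who gets which dose (Statistical Considerations).** "all nine subjects in Cohort 1 will receive the placebo and both 150 and 300 mg doses of the extract"; "all 9 subjects in Cohort 2 will receive the placebo and both 600 and 900 mg doses of the extract". No one receives both 150 and 600 mg.
- **Allocation.** Randomisation Procedure and Blinding assigns sequence within a cohort. Safety and tolerability has the cohorts run one after the other, up to four weeks apart.
- **Weight.** Visit 1, the full PK day, includes "Weight, vital signs (blood pressure, pulse, and temperature"). Table 2 also has weight at screening and at Visits 2a and 3a.
- **Model (Pharmacokinetics of naringenin extract, after Stopping Rules).** "Pairwise comparisons of 150 mg, 600 mg and placebo will be tested with a linear model for each of the parameters". No covariate, log transform or dose normalisation is stated for the model. Apparent oral clearance is defined as dose divided by AUC0-24.

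**The concern.** The crossover protects comparisons within a cohort, such as 150 mg against placebo. It does not protect 150 against 600 mg, which is wholly between subjects and tied to cohort and calendar time. Nothing in the allocation balances body weight across those two doses.

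If naringenin clearance rises with body weight, a heavier Cohort 2 would have lower exposure per milligram. The 600:150 ratio would then fall short of 4 and look like a less than proportional rise; a lighter Cohort 2 would do the reverse. The one body-size measurement that could separate these explanations is already collected but has no stated role in the analysis. With about 12 profiles, an adjustment chosen after seeing the data would carry little weight, so the decision belongs in the plan.

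**Working it through.** **1. The plan's own counts.** The total is 3 subjects × 3 sequences × 2 cohorts = 18, as stated ("A sample of 18 subjects (three subjects in each of three treatment sequences in each of two cohorts")). Full sampling is placed at Visit 1. There, two of the three sequences in each cohort receive 150 or 600 mg, so 2 × 3 = 6 profiles per dose, matching the n=6 in Statistical Considerations. The comparison is 6 v 6 with 12 − 2 = 10 residual degrees of freedom, or 9 with one covariate.

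**2. Range of body size.** At equal height, weight varies by 35/20 = 1.75-fold. At 1.70 m that is 20 × 1.70² = 57.8 kg to 35 × 1.70² = 101.2 kg. If clearance scales with weight to the power 0.75, AUC at one dose varies 1.75^0.75 = 1.52-fold; with power 1, 1.75-fold.

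**3. Assumptions for the simulation (none in the documents).** Height has mean 1.70 m and SD 0.09; BMI is uniform; log AUC = −k × log weight + normal error; k is 0, 0.75 or 1; residual SD is 0.2 to 0.4. True exposure is exactly proportional. Bias in the log ratio is converted to the log-log slope by dividing by ln 4 = 1.386.

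**4. Cohorts from the same population (both BMI 20–35).** Mean weight differs by 15% or more in about 21% of 6 v 6 draws. Chance imbalance moves the dose-normalised ratio by 0.85 to 1.17 (95% range, k = 0.75) or 0.81 to 1.24 (k = 1). The unadjusted interval already allows for this: bias is zero and coverage about 95% at every k and SD tried, with or without weight in the model.

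**5. Cohort 2 heavier, residual SD 0.3.**

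| Cohort 1 v Cohort 2 BMI | k | Slope bias, unadjusted | Coverage, unadjusted | Coverage, adjusted |
|---|---|---|---|---|
| 20–32 v 23–35 (3 units) | 0.75 | −0.06 | 93% | 95% |
| 20–32 v 23–35 (3 units) | 1 | −0.08 | 92% | 95% |
| 20–30 v 25–35 (5 units) | 0.75 | −0.10 | 89% | 95% |
| 20–30 v 25–35 (5 units) | 1 | −0.13 | 86% | 95% |

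Hand check of the third row: the unadjusted dose-normalised ratio averages 0.87, and ln(0.87)/ln 4 = −0.139/1.386 = −0.10. Separate runs on the same general assumptions put the ends of the range at −0.06 to −0.14 and 85–92%, so these cells agree to about 0.01 and one percentage point.

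**6. Width of the interval.** The unadjusted 95% half-width for the slope is about 0.27–0.33 at SD 0.3 and 0.36–0.40 at SD 0.4, well above any bias in step 5.

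**7. Cost of adjusting when weight has no effect (k = 0).** The interval is about 7% wider with balanced cohorts, about 13% wider at a 3-unit BMI difference and up to about 29% wider at 5 units, because weight and dose become correlated.

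**8. Scale of the comparison.** Raw AUC at 150 v 600 mg is expected to differ 4-fold under proportionality. With n=6 per dose, a t-test on raw AUC rejects in about 90% of trials at CV 60% and over 99% at CV 30%, although exposure is exactly proportional. Weight adjustment is informative only once dose has been divided out.

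**The case against.** **A stronger reading that does not hold.** A reader might infer from the 21% figure in step 4 that chance weight imbalance will often produce a false finding of non-proportionality. It will not: between cohorts drawn alike, weight is ordinary between-subject variation already inside the interval. Both cohorts share the same eligibility criteria and recruitment channels, with at most four weeks between them, and the documents give no reason to expect a BMI difference of 3–5 units. A shift is possible, because the cohorts are serial and not randomised against each other, but it is hypothetical.

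**The yardstick.** It is also tempting to set the bias against a slope band of ±ln(1.25)/ln 4 = ±0.16, from the 0.80–1.25 convention. The protocol adopts no such band, and the trial's half-width of 0.27–0.40 exceeds it with or without adjustment.

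**No evidence of a weight effect.** The documents do not show that naringenin clearance depends on weight. The exponent and residual SD are assumptions. This stands, and it is why adjustment should not be the main analysis.

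**A larger gap comes first.** The PK paragraph names no proportionality test. This stands in substance. The nearest thing to one is the clearance comparison, since dose/AUC0-24 is the inverse of dose-normalised AUC. A weight difference could show there, so the point does not vanish, but it should be attached to an explicit dose-normalised comparison.

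**Partial remedy.** One covariate does not remove other differences between cohorts or over calendar time. This also stands.

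**Conclusion.** The point holds as a modest improvement to the analysis, not as a flaw that invalidates it. The documents establish that the proportionality comparison is between subjects, about six per dose, at fixed milligram doses over BMI 20–35, without randomisation between cohorts and without a stated weight term.

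The consequence depends on something the documents cannot settle. With cohorts from one population, leaving weight out costs only precision. With Cohort 2 at 3–5 BMI units higher, exponent 0.75–1 and residual SD 0.3, the slope bias is about −0.06 to −0.14 and unadjusted coverage about 85–92%, restored to about 95% by adjustment. Even then the bias is smaller than the interval's half-width. The primary safety objective is not affected.

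**What to change.** In the paragraph on pharmacokinetics of the extract:

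1. State the main comparison as unadjusted and on the log scale: dose-normalised AUC0-24 and Cmax at 600 v 150 mg (equivalently, the 600:150 ratio judged against 4), and log clearance. As clearance is defined, its log is the mirror image of log dose-normalised AUC0-24, so it is not separate evidence.
2. Pre-specify one supportive analysis adding log body weight on the PK day as the only covariate. That is Visit 1a weight for the six per dose sampled at Visit 1; if subjects first dosed at Visit 2 are also fully sampled, use their Visit 2a weight.
3. Report both ratios with 95% confidence intervals, and mean weight by dose group.
4. Say that adjustment does not address other cohort or calendar-time differences.

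This is wording only: no new data, visits, subjects or change to dosing. The price is one of 10 residual degrees of freedom. If weight has no effect, the adjusted interval is about 7% wider with balanced cohorts and about 13–29% wider when mean BMI differs by 3–5 units. Keeping the adjusted result supportive, beside the unadjusted one, lets the reader see that price.
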